Table 6: Scheduled of Events Group 3a

	Study TTHX-002: Group 3a									
					tudy Da	y				
	0*	7	14	21	28	56	84	168	336*	
		(±1)	(±1)	(±1)	(±1)	(±3)	(±21)	(±21)	(±21)	
Informed Consent	X									
Comprehensive Ocular Examination										
(including slit lamp examination and	SE				SE	SE			SE	
dilated exam of the lens, fundus, and	SE				SE	SE			SE	
vitreous)										
Slit Lamp	SE	SE	SE	SE	SEa	SEa			SE	
Specular Microscopy	SE				SE	SE	SE		SE	
Assessment of Corneal Thickness b	SE		SE	SE	SE	SE	SE	SE	SE	
Best-corrected Visual Acuity	SE	SE	SE	SE	SE	SE	SE	SE	SE	
Intraocular Pressure (IOP)					SE	SE				
measurement										
Pre-injection/procedure	SE	SE	SE	SE						
Post-injection c	SE	SE	SE	SE						
Urine pregnancy test (WOCBP)					X					
Clinical Laboratory Collection										
(Chemistry, Hematology, UA, &										
HbA1c)										
Plasma for ADA	X								X	
Pre-injection										
Plasma for Pharmacokinetics (PK)										
V-FUCHS					X	X				
Study Treatment IC Injection (SE)	X	X	X	X						
Concomitant Medications Review	X	X	X	X	X	X				
Assess Adverse Events	X	X	X	X	X	X				

OU=both eyes, SE=Study Eye, V-FUCHS=Visual Function and Corneal Health Status

Note: Unless otherwise specified assessments to be performed prior to study treatment injection, if applicable

\*Day 0 pretreatment assessments may be obtained within the 7 days prior to Day 0 (if screening assessment within 7 days, do not need to be repeated)

<sup>a as part of Comprehensive Eye Examination

<sup>b measured by AS-OCT (preferred) if AS-OCT not available, Pentacam, or Ultrasound Pachymetry is to be used (Note: subjects must be assessed using the same modality throughout the study)

<sup>c IOP pre-injection and then post-injection every 30 to 60 minutes until less than at least 5 mmHg higher than pre-injection IOP

\*End of Study Visit (EOS) may be performed any time after Day 168; if the Day 336 visit, if the subject has already completed the study, the subject should be contacted and asked to provide a plasma sample for ADA; any subject who did not have gradeable specular images at their most recent visit should be re-imaged and gradeable images obtained

Clinical Study Protocol TTHX-002 Amendment 7.0: September 22, 2022

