#### **Study Treatment Group 4:**

On Day 0, subjects will undergo DWEK/ DSO and will receive TTHX1114 (100ng [100mcL]) at the time of the surgical procedure and then weekly injections x 3. Subjects who have not sufficiently recovered by Day 28, may receive an additional dose of TTHX1114 following discussion with the Medical Monitor.

Study subjects will then return for follow-up on Day 1 (the day after DWEK/DSO) and subsequent study treatment administration on:

- Day 7
- Day 14
- Day 21

Follow-up visits will occur on:

- Day 28\*
- Day 56

\* Subjects who have not sufficiently recovered by Day 28, may receive an additional dose of TTHX1114 following discussion with the Medical Monitor. In this context, Medical Monitor refers to Sponsor (or designee). If the Sponsor (or designee) agrees that the study subject can receive the 5th TTHX1114 administration, all assessments scheduled for Day 21 should be repeated on Day 28 and an unscheduled visit conducted on or around Day 35 when all assessments scheduled for Day 28 should be conducted.

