# **Study Treatment Group 3a:**

Subjects in Group 3 may be allowed to "roll-over" to a TTHX1114 regimen of up to 4 weekly injections of TTHX1114. To be eligible for Group 3a, subjects must

- continue to be eligible for the study (e.g., have a suitable fellow eye and not have had any severe suspected adverse reactions)
- not have achieved adequate restoration of the endothelium (anatomic recovery) by the anticipated timepoint following the DWEK/DSO procedure (e.g., Day 56 or 84)
  - Note: the trigger for roll over to Group 3a may be earlier if the time to anatomic recovery observed in Group 2 or 3 is sooner

Subjects who had previous participated in Group 3 will receive up to 4 weekly study treatment administrations.

- Day 0
- Day 7
- Day 14
- Day 21

Follow-up visits will occur on:

- Day 28
- Day 56

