#### 6.1 Subject Screening and Enrollment

Potential study participants will be asked to sign an Informed Consent Form (ICF) prior to any study assessments. Screening should be completed within approximately 28 days of Study Day 0 (unless approved by the Medical Monitor); non-qualifying screening assessments (e.g., specular microscopy) and screening assessments outside this window may be repeated. Screening assessments will include:

Assessment of study eligibility

Confidential and Proprietary

Amendment 7.0: September 22, 2022

- Medical and ocular history
- BCVA assessment
- Comprehensive ocular examination (including slit lamp biomicroscopy and dilated examination of lens, fundus, and vitreous)
- Specular microscopy (including images of the central and peripheral cornea)

All potential study subjects will be provided with a unique Subject ID Number (Subject ID) at the time of providing written informed consent. The Subject ID will consist of a unique 6-digit number (3-digit site number and a 3-digit subject number, separated by a hyphen [-]).

Figure 3: Subject ID Numbering

Subject ID Number						
Site Number			=	Subject Number		
9	9	9	-	2	0	1

For example, Subject ID 101-201 = The first participant consented at Site 101; 103-203 = The third participant consented at Site 103

Once a Subject ID number has been issued, it cannot be reused. Potential subjects may have repeat eligibility assessments (if appropriate) or be rescreened, following discussion with the Medical Monitor (or designee).

Subjects who had participate in Study TTHX-001 will receive a new Subject ID number for identification in Study TTHX-002. Subjects who "roll-over" to Group 1a or Group 3a will retain the same Subject ID number.

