#### 6.4.10 Urine Pregnancy Test

WOCBP must be tested prior to the start of study treatment and after the completion of study treatment to confirm a continued non-pregnant state. Commercially available urine dip-stick pregnancy tests are acceptable.

Clinical Study Protocol TTHX-002

Confidential and Proprietary

Amendment 7.0: September 22, 2022

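### Group 3a starts a new injection course with no scheduled pregnancy test at Day 0; the last scheduled result is nominally 28 days old at a Day 56 roll-over, in line with first doses, but 56 days old at Day 84

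*Combined protocol and SAP*

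**What the plan says.** - **Table 6 (Group 3a).** Injections are marked on Days 0, 7, 14 and 21. The row "Urine pregnancy test (WOCBP" has one mark, at Day 28, and its Day 0 cell is empty. Day 0 does carry informed consent and a pre-injection sample in the row "Plasma for ADA". A footnote adds flexibility: "Day 0 pretreatment assessments may be obtained within the 7 days prior to Day 0".
- **Table 3 (Group 3).** The pregnancy test is marked at Screening and at Day 28, and at no later visit.
- **Table 5 (Group 1a).** The test is marked at Day 0 and Day 28. Table 1 (Group 1) has no pregnancy test.
- **Section 6.4.10.** "WOCBP must be tested prior to the start of study treatment and after the completion of study treatment". It does not say whether a roll-over course counts as a new start of treatment.
- **Section 4, Study Treatment Group 3a.** Roll-over is for subjects without adequate endothelial recovery by the expected time "following the DWEK/DSO procedure (e.g., Day 56 or 84"), and "the trigger for roll over to Group 3a may be earlier". Subjects must still be eligible for the study.
- **Section 6.1.** Subjects who roll over "to Group 1a or Group 3a will retain the same Subject ID number".

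**The concern.** Table 6 treats Group 3a as a separate course in several ways: its day count restarts at 0, it takes consent, it repeats a pre-injection sample, and it has its own test after the last injection. The matching test before the first injection is missing. No visible text says that the Group 3 results carry over, and none schedules a test before re-dosing. A site working from Table 6 could give a second course of up to four injections on a result several weeks old. A pregnancy already present at Group 3a Day 0 would then meet its next scheduled test only after the last injection.

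Pregnancy is a reason to stop study treatment (Sections 5.3 and 6.6), so a current result bears directly on the decision to re-dose. Contraception (Section 6.3.3) and notification by the subject (Section 6.6) remain as safeguards, but neither is a test. Only participant safety is at stake. No estimate, endpoint or analysis set depends on it.

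**Working it through.** The protocol states no maximum age for a pregnancy test, so there is no planned figure to reproduce. The check is the age of the last scheduled result at each injection.

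**Inputs**
- Last Group 3 test: Day 28 ± 3, so Days 25 to 31 (Table 3).
- Roll-over examples: Day 56 ± 3, so Days 53 to 59; Day 84 ± 21, so Days 63 to 105 (Section 4 for the days, Table 3 for the windows).
- Group 3a injections: Days 0, 7, 14 and 21, the last three ± 1 (Table 6).
- Screening: within approximately 28 days of Day 0, longer with Medical Monitor approval (Section 6.1).
- Assumption: the first Group 3a injection is given at the roll-over visit.

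**Age at the first Group 3a injection** = injection day − test day
- Day 56: nominal 56 − 28 = 28 days; shortest 53 − 31 = 22; longest 59 − 25 = 34.
- Day 84: nominal 84 − 28 = 56 days; shortest 63 − 31 = 32; longest 105 − 25 = 80.

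**Age at the fourth Group 3a injection** (nominal)
- Day 56 roll-over: 28 + 21 = 49 days.
- Day 84 roll-over: 56 + 21 = 77 days.

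**What the protocol accepts elsewhere**, taking Screening at Day −28
- First dose in Groups 3 and 4 (Tables 3 and 4 mark no Day 0 test): 0 − (−28) = 28 days.
- Day 21 injection in Groups 2 and 4: 21 − (−28) = 49 days.
- Optional fifth dose in Group 4 at Day 28: 28 − (−28) = 56 days. The Day 28 test does not precede this dose, because Section 4 calls for "an unscheduled visit conducted on or around Day 35 when all assessments scheduled for Day 28 should be conducted".

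| Injection | Protocol's own interval | Day 56 roll-over | Day 84 roll-over |
|---|---|---|---|
| First of a course | about 28 | 28 | 56 |
| Fourth (Day 21) | about 49 | 49 | 77 |

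The Day 56 case matches existing practice at both points. The Day 84 case adds 56 − 28 = 28 days at each, and its 77 days also exceeds the 56 days of the Group 4 fifth dose.

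**With a Group 3a Day 0 test**, taken on Day −7 to Day 0
- First injection: 0 to 7 days.
- Fourth injection: 20 − 0 = 20 to 22 + 7 = 29 days.

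**Women affected.** Table 7 plans 20 subjects for Group 3. The protocol gives no share of women of childbearing potential. At an assumed 0 to 10% this is 20 × 0 = 0 to 20 × 0.10 = 2 women, before allowing for how few would roll over.

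**The case against.** - **The age of the test is often ordinary for this protocol.** A first-ever 100 ng dose in Groups 3 and 4 can rest on a Screening test about 28 days old. This stands: a Day 56 roll-over is nominally no worse, and only later roll-over clearly exceeds the norm. A 7-day limit for Group 3a would also be stricter than the rule for first doses. The case for it is that the visit already exists and the test is cheap.
- **The roll-over check may already include a test.** Section 4 requires continued eligibility, and Section 6.1.3 requires registration, approval and an eligibility checklist. The criteria themselves (Sections 5.1 and 5.2) are largely not visible, nor is the text of Section 6.2.1, and the site worksheets (Section 6.5.2) are not in the document. This stands as a limit on the finding. The visible examples of continued eligibility are a suitable fellow eye and no severe suspected reactions; neither is a test.
- **A reader might infer a breach of Section 6.4.10, or that these women are untested.** The document does not support this. They have Group 3 tests at Screening and Day 28 and remain the same subjects under the same number, so the section is met if read per subject. If it is read per course, the text already requires the test and only the table cell is missing.
- **A reader might take Table 5 as proof of an omission in Table 6.** It is not: Group 1a needs a Day 0 test because Group 1 has none. The repeated antibody sample is weak evidence too. It serves immunogenicity, and Table 6 leaves clinical laboratory and pharmacokinetic sampling blank.
- **The ranges are not hard bounds.** The roll-over days are examples, and rolling over between Day 28 and Day 56 shortens the interval. Under Section 6.1.3 product is shipped after approval, which could lengthen it. Both points stand.

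**Conclusion.** The gap holds as a minor, optional improvement and is not an error in the plan. The visible schedule has a test after the Group 3a course but none before it. At a Day 56 roll-over the last scheduled result is about as old as the protocol accepts for first doses. At Day 84 it is nominally twice that.

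This rests on dosing at the roll-over visit, on the Day 56 and Day 84 examples, and on the undisclosed eligibility criteria containing no test. If they do contain one, only the table needs aligning. The practical reach is small: at the assumed share, 0 to 2 of the 20 planned Group 3 subjects before roll-over, in a group that the sponsor may choose not to open. Fetal risk cannot be judged from the document, because the text of the non-clinical, risk and dose-rationale sections is not visible.

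**What to change.** 1. In Table 6, mark a pre-injection urine pregnancy test for women of childbearing potential at Day 0, within the table's 7-day allowance, as Table 5 already does for Group 1a.
2. Require a negative result before the first Group 3a injection.
3. State in Section 6.4.10 that the pre-treatment test applies to each treatment course, including roll-over.

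The change is one schedule cell and a short addition to Section 6.4.10. The running cost is one commercially available dip-stick per eligible woman, at a visit that already includes consent and a pre-injection sample.

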# LIST OF ABBREVIATIONS

ADA	Anti-Drug Antibody
AE	Adverse Event
AS-OCT	Anterior Segment Optical Coherence Tomography
BCVA	Best Corrected Visual Acuity
CCT	Central Corneal Thickness
CEC	Corneal Endothelial Cell
CED	Corneal Endothelial Dystrophies
CIARC	Cornea Image Analysis Reading Center
Con Med	Concomitant Medication
CRF/ eCRF	Case Report Form/ electronic Case Report Form
CRO	Contract Research Organization
DHHS	Department of Health and Human Services
DLT	Dose limiting toxicity
DMEK	Descemet Membrane Endothelial Keratoplasty
DSEK	Descemet Stripping Endothelial Keratoplasty
DWEK/ DSO	Descemet Stripping Without Endothelial Keratoplasty/Descemet Stripping Only
ECD	Endothelial Cell Density
EDC	Electronic Data Capture
eFGF-1	engineered FGF-1
ETDRS	Early treatment diabetic retinopathy study
FDA	Food and Drug Administration
FE	Fellow Eye
FECD	Fuchs Endothelial Corneal Dystrophy
FGF	Fibroblast Growth Factor
GAT	Goldmann Applanation Tonometry
GCP	Good Clinical Practice
HED	Human Equivalent Dose
IC	Intracameral
ICF	Informed consent form
ICH	International Conference on Harmonisation
IOP	Intraocular pressure
IRB	Institutional review board
ITT	Intent to Treat
IUD	Intrauterine device
LOCF	Last Observation Carried Forward
MMRM	Mixed Model Repeated Measures
MRSD	Maximum Recommended Starting Dose
NOAEL	No Observable Adverse Event Level
OEDP	Optional Extended Dosing Period
PAD	Pharmacologically Active Dose
PK	Pharmacokinetic Post
PP	Per Protocol
SAE	Serious Adverse Event
SAR	Suspected Adverse Reaction
SE	Study Eye
TM	Trabecular Meshwork
V-FUCHS	Visual Function and Corneal Health Status
WOCBP	Women of Childbearing Potential
wtFGF-1	Wild type FGF-1
wir'dr-1	who type POP-1

Clinical Study Protocol TTHX-002 Amendment 7.0: September 22, 2022

#### 1. INTRODUCTION

#### 1.2 Corneal Endothelial Dystrophy

Corneal endothelial hypocellularity driven by corneal endothelial cell (CEC) loss due to trauma, surgical damage, or corneal endothelial dystrophies (CED) can have a significant effect on vision and a high impact on quality of life. Corneal endothelial cell loss or low CEC counts contribute to poor outcomes of ocular surgery, including cataract surgery. Fuchs Endothelial Corneal Dystrophy (FECD) is the most common driver of corneal transplantation [1], with 17,468 endothelial keratoplasty procedures performed in the US in 2008 [2]. Corneal endothelial dystrophies have been estimated to affect approximately 4% of the US population over the age of 40 [3] although more recent estimates using claims data and more stringent criteria put the overall prevalence of CED at 0.13% and the prevalence of FECD at 0.078% [4]. Corneal endothelial hypocellularity secondary to surgery or trauma is an infrequent but significant complication that can lead to corneal transplantation and contributes to visual impairment.

#### 1.3 Treatment Options

Beyond symptomatic treatment using various pharmacologic therapies, the only treatment option for patients with CED is the transplantation of CECs either as a whole corneal transplant or transplantation of the endothelial layer via a variety of endothelial keratoplasty procedures, including Descemet Stripping Endothelial Keratoplasty (DSEK) [5] and Descemet Membrane Endothelial Keratoplasty (DMEK) [6]. Even after transplantation, the number of CECs in the transplant continues to decrease [7] and repeat transplants are sometimes needed. Corneal transplantation is an option of last resort as donor tissue is in short supply, the surgery requires a

Confidential and Proprietary

Amendment 7.0: September 22, 2022

highly skilled surgeon, and there is a significant risk of complications, transplant rejection and long-term failure. Corneal transplantation in patients with CED has a significantly higher long-term failure rate than transplantation for keratoconus and approximately 34% of transplants will fail in the first 10 years (vs 11% for keratoconus) [8].

#### Descemetorhexis without Endothelial Keratoplasty (DWEK) 1.3.1

# 2. BACKGROUND INFORMATION

# 2.1 Investigational Product TTHX1114(NM141)

Please refer to the Pharmacy Manual for study treatment storage, handling, and preparation instructions.

Confidential and Proprietary

Amendment 7.0: September 22, 2022

# 2.2 Summary of Nonclinical Studies and Clinical Trials

# 2.2.1 Nonclinical Studies

#### 2.2.2 Clinical Trials

This is the second clinical trial of TTHX1114. The first clinical trial (Study TTHX-001) is a randomized, placebo-controlled, masked study. As clinical safety data becomes available, the Investigator Brochure (IB) will be updated and provided to all Investigators involved in clinical trials of TTHX1114. Please refer to the current version of the IB for the most up to date safety information related to clinical trials of TTHX1114.

Please refer to the current version of the Investigator Brochure for the most current data related to TTHX1114 clinical trials.

#### 2.3 Potential Risks and Benefits

[figure not shown]

Confidential and Proprietary

Amendment 7.0: September 22, 2022

# 2.4 Rationale for Dose Selection

Amendment 7.0: September 22, 2022

# 2.5 Statement of Compliance

This study will be conducted according to the protocol and in compliance with Good Clinical Practice (GCP) which have their origins in the Declaration of Helsinki and with all other applicable regulatory requirements.

#### 2.6 Study Population

The study population will consist of men and women aged ≥ 18 years with a confirmed diagnosis of FECD who will undergo DWEK/DSO.

#### 3. TRIAL OBJECTIVES AND PURPOSE

The primary objective of this clinical trial is to evaluate the safety and efficacy of TTHX1114 in the setting of DWEK/DSO. The primary efficacy endpoint will include CEC counts/ characteristics and BCVA following the surgical procedure.

#### 4. TRIAL DESIGN

This is an open-label, multi-center study in which up to approximately 50 subjects with FECD who are scheduled for DWEK/DSO will be enrolled. Study subjects will be assigned to Study Treatment Group based on the Group(s) open at the time of treatment of the primary (first) eye; if a subject elects to have an eligible second (contralateral) eye treated, that "fellow" eye will be treated based on the Group(s) open at the time. The number of subjects per group in the study and per study treatment is summarized below in Table 7.

Amendment 7.0: September 22, 2022

Note: the study was amended to allow treatment of the contralateral eye. To avoid ambiguity the eye that was treated first will be referred to as the Study Eye (SE); the contralateral eye will be referred to as the Fellow Eye (FE).

**Table 7: Study Groups and Number of Subjects** 

	TTHX1114	4 Regimen		
	Day	Dose	Number of Subjects	
Group 1	N/A	N/A	8 (Closed after 1 enrolled)	
	Day -3	10ng		
	Day 0	50ng	9.16	
Group 2	Day 7	10ng	8-16 (Closed after 9 enrolled)	
•	Day 14	10ng		
	Day 21	10ng		
Group 3	Day 0	100ng	20	
Group 4	Day 0	100ng	20	
	Day 7	30 or 50ng		
	Day 14	30 or 50ng		
	Day 21	30 or 50ng		
Group 1a	Weekly x 5	30 or 50ng	NA	
Group 3a	Weekly x4	30 or 50ng	NA	
·		 	up to 50	

[figure not shown]
Subject will be consented and screened for eligibility during the screening period prior to the scheduled DWEK/DSO procedure.

The study schema is presented in Figure 1 and Figure 2.

Confidential and Proprietary

Amendment 7.0: September 22, 2022

Figure 1: Study Treatment Schema

\*Subjects who have not sufficiently recovered by Day 28, may receive an additional dose of TTHX1114 following discussion with the Medical Monitor

Eligible subjects who do not wish to receive investigational product or who do not have a qualifying Fellow Eye will be assigned to Treatment Group 1.

Following preliminary safety and tolerability assessment of the 50ng IC injection in Group 2, Trefoil may elect to open Group 3 and Group 4

[figure not shown]
- Group 3 in which eligible subjects will be given a "1 and done" dosing regimen in which TTHX1114 will be administered as a 100ng/100mcL volume injection at the time of DWEK/DSO
- Group 4 in which eligible subjects will be given a 100ng/100mcL volume injection at the time of DWEK/DSO and then weekly injections of 30 or 50ng (30 or 50mcL) x3. Subjects in Group 4, who have not sufficiently recovered by Day 28, may receive an additional dose of TTHX1114 following discussion with the Medical Monitor

Following preliminary safety and efficacy evaluation in subjects who received TTHX1114, Trefoil may open enrollment in Groups 1a and 3a in which TTHX1114-naive subjects in Group 1 and subjects in Group 3 may be allowed to "roll-over" to a TTHX1114 regimen of up to 5 weekly injections of TTHX1114. To be eligible for Group 1a or Group 3a, subjects must continue to be eligible for the study (e.g., have a suitable fellow eye and not have had any severe suspected adverse reactions.

\* End of Study Visit (EOS) may be performed any time after Day 168; if the Day 336 visit has already been completed subjects should be contacted and asked to provide a plasma sample for ADA; any subject who did not have gradeable specular images at their most recent visit should be re-imaged and gradeable images obtained

Amendment 7.0: September 22, 2022

Figure 2: Group 1a and Group 3a Study Treatment Schema "Roll-over"

\* End of Study Visit (EOS) may be performed any time after Day 168; if the Day 336 visit has already been completed subjects should be contacted and asked to provide a plasma sample for ADA; any subject who did not have gradeable specular images at their most recent visit should be re-imaged and gradeable images obtained

